1.0 Objectives

1.1 Describe the purpose, specific aims, or objectives of this research. Specifically, explain why it is important to do the study.

Response: This research aims to evaluate the impact of subtle vibrations applied to the ankles, on gait and mobility in older adults. Participants will not consciously perceive the vibrations after initial set-up. More specifically-

Impact of device on gait and mobility

 Older adults' perception of device function, wearability, and impact on mobility confidence

2.0 Background

2.1 Provide the scientific or scholarly background, rationale, and significance of the research based on the existing literature and how it will contribute/fill in gaps to existing knowledge.

Response: The research protocol outlines the evaluation of stochastic resonance (SR) ankle bracelets in improving mobility in older adults. The concept is that improved mobility would be associated with reduction in falls. Falls in the elderly are a significant public health concern, being the leading cause of injury, hospitalization, and death in this population. Although the elderly make up about 12% of the U.S. population, they account for 75% of deaths related to falls. Approximately one in four individuals over the age of 65 experience a fall annually, with many falling more than once. The healthcare costs associated with falls are staggering, with current estimates of combined direct and indirect costs exceeding \$80 billion. Contributing to these costs are hospital stays, medical equipment, and rehabilitation, which underscores the need for effective preventative measures. The risk factors for falls among older adults include vision problems, muscle weakness, and a decline in somatosensory function. Among these, the loss of tactile and proprioceptive sensations has been identified as a critical predictor of falls. Stochastic resonance (SR) is a phenomenon where the addition of a certain level of noise can enhance sensory signal detection. In this context, SR-based devices, such as vibrating insoles, have been explored for their potential to improve balance and reduce postural sway, which could ultimately reduce fall risk in elderly populations.

Previous studies have shown promising results. For example, SR has been shown to enhance tactile sensation in human subjects. Later studies extended this work, demonstrating that SR could reduce the sensory detection threshold in elderly individuals and those with conditions like diabetic neuropathy and stroke. Further investigation of SR insoles participants found that the insoles reduced postural sway in the elderly. These results suggest that SR could be an effective tool for enhancing mobility and in association reduce falls in older adults. Despite these promising findings, important questions remain unanswered.

2.2 Include complete citations or references:

Response:

3.0 Study Design

3.1 Describe and explain the study design (e.g., case-control, cross-sectional, ethnographic, experimental, interventional, longitudinal, and observational). Indicate if there is randomization, blinding, control group, etc. If randomizing, explain how this will be achieved.

This is a pilot, observational study with 20 volunteers at Jefferson's Ferry Independent Living. Before the Accelera ankle bracelets are applied, participants will complete a pre-study questionnaire. They will then complete 3 tests that the Centers for Disease Control (CDC) recommends for fall risk assessment, namely the chair stand test, 4-point balance test, and timed up and go test, while using their usual mobility assist devices. If the participants provide optional consent, they will undergo video-based gait/mobility analysis of information derived from the HIPAA compliant Onform video recording app, while they are using their usual mobility

assistance devices, if any. In other words, a video recording is made with the app and stored on the apps' HIPAA compliant platform. With the faces obscured, measurements of their gait/mobility will be performed using additional programs as indicated in the Data section. After bracelet application, volunteers will then be encouraged to resume their normal ambulation-(while using their usual mobility assistive devices) for about 30 minutes at the study location as described below. The same 3 tests will be repeated after 30 minutes, along with a post-study questionnaire, and if they consented to video recording above, then repeat videorecording with the Onform video recording app would be performed. With the faces obscured, measurements of their gait/mobility will be performed using additional programs as indicated in the Data section. At this point, the ankle bracelets will be removed – with the subjects having worn them for about 1 hour total. There will be an additional up to 1 hour for completion of the pre- and post-study questionnaires, for a total study session duration of about 1.5 - 2 hours. At each session, we will apply these bracelets to a minimum of 1 patient per session. These sessions will occur at the Wellness Center/gym or other designated area at Jefferson's Ferry 1x per week, with a minimum of one patient for up to 8 patients/week if no holidays, until 20 patients have completed the study. To address infection control, a disposable sock will provide a physical barrier between the device and patient, while still allowing the patient to feel the stochastic resonance.

3.2 Include the number of subjects and the power analysis. If applicable, indicate your screen failure rate, i.e., how many subjects you expect to screen to reach your target sample.

Response: 20 volunteers will be enrolled. The study would continue until 20 volunteers are enrolled and complete all non-optional parts of the single study session.

3.3 Indicate the duration of the subject participation including long-term follow-up.

Response: A single study session. There is no long-term follow-up in this study.

3.4 Indicate whether you are specifically recruiting or targeting any of the following special populations in your study using the checkboxes below.

Response: n/a

Minors (under 18 years old)

Adults unable to consent

Pregnant women

Protoco	ol Title (Running Head):
	Prisoners
	Indicate if you will include minorities (American Indians, Alaskan Native, Asian, Native an, Pacific Islander, Black [not of Hispanic origin] and Hispanic) as Federal mandates that you include minorities unless you can justify their exclusion.
Respor	nse:
\boxtimes	Yes
	No, Justify:

3.6 Indicate whether you will include non-English speaking individuals in your study. Provide justification if you will specifically exclude non-English speaking individuals. Review https://www.stonybrook.edu/research-compliance/Human-Subjects/sops for the SBU policy on inclusion of non-English speakers (section 17.8). Following approval of the English version, you must submit the translated version of the materials with the attestation of the translation.

Response: Non-English speakers will be excluded to assure understanding of verbal instructions in English as well as enable completion of the survey.

3.7 Describe the data analysis plan, including any statistical procedures.

NOTE: If we are a lead site for a multi-site study include the total number of subjects that will be enrolled, or records that will be reviewed across all sites. This section applies to both quantitative and qualitative analysis.

Response: The data of participants who meet the inclusion criteria will be collected during study visits and recorded directly by study staff. Only the consents will have the participant's names. There will be no linking of the participant to subject ID. Hence, all data will be de-identified and stored using unique study identifiers to protect participant privacy. The data will be securely stored on password-protected, encrypted servers at Stony Brook Medicine to ensure compliance with privacy and confidentiality standards.

If the participants choose to have their mobility evaluated by the research team with the video recording app, then their videos would be uploaded to the HIPAA compliant platform of the app. The first name used for the app would be the 1st digit of their assigned code and the last name would be the last digit of their assigned code. Their faces would be obscured by taking a video from the chin/neck down.

Descriptive Analysis:

Descriptive univariate statistics will be conducted to summarize the demographic and performance characteristics of the study population, including device sensory thresholds, gait/mobility using a mobility videorecording app (optional, see below) before and while wearing the ankle bracelets, pre- and post-study questionnaires, and performance before and while wearing the ankle bracelets on the 3 CDC STEADI tests (the chair stand test, 4 point balance test, and timed up and go test). Multivariate analysis would also be performed.

Videos uploaded on the Onform app with participants' faces obscured would then be analyzed with additional feature extraction, analytics, and statistical programs. This would include optical character recognition programs to analyze the joint angles numbers that the video recording provides. Outside of the app, parts of the video will be cropped, the stick figure that the Onform app generates will be highlighted, and the contrast and lighting of the video will be adjusted to make the subject look like a shadow, ie s no features of the subject (such as clothing, gender, skin color, etc.) can be recognized. Programs such as ImageJ will be used for feature extraction. Python/R will be used to pull the data from the videos/cropped images. Python/R/excel will be used for statistical analysis of gait/mobility parameters, such as joint angles, stride time, stance time, swing time, cadence, stride length, step width, and foot angle, etc

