13.0 Withdrawal of Subjects			
□ N/A: This study is not enrolling subjects. This section does not apply.			
13.1 Describe anticipated circumstances under which subjects may be withdrawn from the research without their consent.			
Response: if the participant is unable to participate in the study during the study session for any reason, including inability to walk, they would be withdrawn from the study			

13.2 Describe any procedures for orderly termination.

NOTE: Examples may include return of study drug, exit interview with clinician. Include whether additional follow up is recommended for safety reasons for physical or emotional health.

Response: n/a

13.3 Describe procedures that will be followed when subjects withdraw from the research, including retention of already collected data, and partial withdrawal from procedures with continued data collection, as applicable.

Response: If a subject withdraws on the day of the study before information is deidentified, their data will be removed. This includes removal of data/videos from the Onform app if they had opted in to participate.

13.4 Describe what will happen to data already collected.

Response: Data can only be discarded at the time of the study session if the participant requests. After that, we would not be able discard it as there is no matching between the person who signed the consent and the random participant/subject ID. As we are not keeping any picture of the participants and faces will be obscured on the Onform video recording, after the session, we would not be able to delete the videos.

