14.0 Risks to Subjects

14.1 Describe if any subjects will be withdrawn from therapeutic procedures or drugs (e.g., washout periods) prior to, or during, their participation in the study.

Response: n/a

14.2 List the reasonably foreseeable risks, discomforts, to the subjects related to their participation in the research. Consider physical, psychological, social, legal, and economic risks.

NOTE: Breach of confidentiality is always a risk for identifiable subject data.

- Response: Mild skin irritation from wearing the device.
- Temporary muscle fatigue from mobility exercises.
- Dizziness or imbalance while adjusting to the device.
- Minimal risk of falling and sustaining any injury from the fall, with or without device. The study will be conducted in a monitored setting with a healthcare provider who is also a part of the research staff available.
- Loss of confidentiality

•	Since this is a research study, not all risks may be known at this time; there may be unforeseen risks associated with study participation.
14.3 proced	Describe the probability, magnitude, duration, and reversibility of the risks and the dures to minimize these risks.
-	onse: Participants will be asked to stay in the fixed area at Jefferson's Ferry, e.g. wellness /gym, for the approximate 1.5 - 2-hour duration of the study.
14.4	Describe procedures being performed to monitor subjects for safety.
-	onse: Participants will be asked to stay in the fixed area at Jefferson's Ferry, e.g. wellness /gym, for the approximate 1.5 - 2-hour duration of the study.
	If the study poses risks to an embryo or fetus should the subject be or become pregnant, ill you minimize the risk of a pregnancy occurring during the course of the study? (Select apply.)
	Counseling on birth control and /or abstinence
	Pregnancy test during the study
	Pregnancy test prior to initiation of the study
	Other
14.6 subjec	If applicable, describe possible risks to others who are not subjects (e.g., partner of a two is administered a study drug).
Respo	nse: n/a
14.7	Provisions to Monitor the Data to Ensure the Safety of Subjects
□ OR is	N/A: This study is not enrolling subjects OR is limited to records review procedures only a minimal risk study. See SBU SOPs section 3.6 for a list of the procedures that are

generally considered to be minimal risk: https://www.stonybrook.edu/research-compliance/Human-Subjects/sops).

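### Accruing to 20 completers, with unclear rules on withdrawn participants' data, can drop people who cannot finish with the bracelets on and so risks favouring the device

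*Protocol*

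**What the plan says.** Section 3.2 of the protocol gives the sample size as "20 volunteers will be enrolled" and then adds: "The study would continue until 20 volunteers are enrolled and complete all non-optional parts of the single study session". Section 3.1 repeats the rule: weekly sessions run "until 20 patients have completed the study". Under 3.1 and 7.1 only the video recording is optional, so the three repeat tests with the bracelets on are among the parts that must be completed.

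Section 13.1 covers withdrawal without the subject's consent, and its condition is broad: "unable to participate in the study during the study session for any reason, including inability to walk, they would be withdrawn from the study". It does not distinguish the time before the bracelets are applied from the time after.

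Two neighbouring sections deal with the data. Section 13.3: "If a subject withdraws on the day of the study before information is deidentified, their data will be removed". Section 13.4: "Data can only be discarded at the time of the study session if the participant requests".

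Among the foreseeable risks, section 14.2 lists "Dizziness or imbalance while adjusting to the device". Section 14.8 has falls and device-related adverse events recorded during participation, with safety data going to the monitor after every five completers.

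**The concern.** The study asks whether the device changes gait and mobility, and section 3.7 compares each person before and while wearing it. A participant who does the baseline tests, is fitted, and then becomes too dizzy or unsteady to do the repeat tests bears directly on that question. As the rules stand, this person can be withdrawn, may have the baseline data deleted, and is in effect replaced by someone who can finish. That is selection on something close to the outcome, and there is no control arm in which the same selection would show up.

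The matter belongs in the protocol. Accrual, withdrawal and deletion are protocol rules, and section 3.7 keeps no link between the person and the study code. A later analysis plan could not bring back data that had been removed.

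**Working it through.** **The plan's own figure.** The only figure is 20. No effect size, SD, power or withdrawal rate accompanies it, so there is nothing to reproduce.

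**Reading the rules in sequence.**

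1. Accrual stops at 20 completers (3.1, 3.2), so each non-completer is in effect replaced.
2. Completion requires the repeat tests with the bracelets on (3.1, 7.1), so all 20 counted will have managed them.
3. Withdrawal under 13.1 can happen after fitting as well as before.
4. For a participant withdrawn by staff, 13.3 can be read as deleting the data, while 13.4 restricts discarding to the participant's request. The two do not settle what happens to baseline or partial results.

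**How much this could matter.** All inputs here except the 20 are assumptions. Let d be the proportion withdrawn after fitting, and ρ the correlation between tolerance of the session and the change while wearing the device (positive change means better). Suppose the least tolerant fraction d withdraws, both quantities are normal, and the device has no true effect.

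- Enrolment needed for 20 completers: 20/(1−d), rounded up.
- Chance of at least one replacement: 1−(1−d)^20.
- Bias in mean change, in SDs of the change: ρ·φ(z_d)/(1−d), where z_d is the d-quantile of the standard normal and φ its density.

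For d = 10%: z_d = −1.282, φ = 0.1755, and 0.1755/0.9 = 0.195. With ρ = 0.3 the bias is 0.058; with ρ = 0.5 it is 0.097.

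| d (assumed) | Enrolled for 20 completers | At least one replacement | Bias, ρ = 0.3 | Bias, ρ = 0.5 | Bias, ρ = 1 (extreme) | False benefit, ρ = 0.3 to 0.5 |
|---|---|---|---|---|---|---|
| 5% | 21.05 → 22 | 1−0.358 = 0.642 | 0.033 | 0.054 | 0.109 | 3.2 to 4.2% |
| 10% | 22.22 → 23 | 1−0.122 = 0.878 | 0.058 | 0.097 | 0.195 | 4.2 to 6.1% |
| 20% | 25.0 → 25 | 1−0.012 = 0.988 | 0.105 | 0.175 | 0.350 | 6.6 to 11.7% |

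The last column is the simulated chance of a significant benefit when there is none (20,000 runs, 20 completers, paired t-test, nominal 2.5% in that direction). The protocol names no test; the t-test only gives a scale. Simulated mean biases agreed with the formula to within about 0.004 SD.

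**Boundary cases.** With d = 0 or ρ = 0 the bias is zero. With ρ = −0.3 it reverses: −0.033, −0.058 and −0.105 SD at 5, 10 and 20%.

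**For comparison.** Twenty pairs give 80% power for a change of about 0.66 SD (paired t-test, two-sided 0.05). At moderate ρ the bias is well below that, though not negligible at 20% withdrawal.

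**The case against.** A reader might infer that the 20 analysed are by construction those who tolerated the bracelets, so that the result is biased in the device's favour. The documents do not support that, for these reasons:

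- The protocol names no analysis set. Section 3.2 says when accrual stops, not who is analysed, and analysis sets are commonly left to an analysis plan.
- Section 13.1 says that a person is withdrawn, not that the data are deleted. On the wording of 13.4, a staff withdrawal alone would not erase anything.
- Performing badly is not the same as being unable to participate. Someone who is slower or less steady but attempts the repeat tests stays in.
- Withdrawals before fitting, or for unrelated reasons, do not shift the before/while-wearing change in this way. Section 4.2 already excludes people who cannot walk that day, so the inability to walk in 13.1 may partly mean people found unfit on arrival. Section 14.2 attributes muscle fatigue to the mobility exercises, not to the device.
- The session is short, so withdrawals may be few or none. Falls and device-related adverse events are recorded in any case.

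These points stand, and they make the bias conditional and its size unknown. They do not remove the gap. Nothing in 13.1 confines withdrawal to the time before fitting, 13.3 can still be read as deleting the data, and an adverse-event record neither puts the person into the mobility comparison nor gives the number who could not finish.

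**Conclusion.** The concern holds as a risk, not as an established bias. Followed as written, sections 3.1, 3.2, 13.1 and 13.3 allow people who cannot finish with the device on to be replaced and possibly erased, and 13.4 contradicts the erasure. The mobility result would then lean towards the device if withdrawals occur after fitting and are linked to a poor response to it.

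The size cannot be determined from the documents. The modelled figures rest on assumed withdrawal rates, assumed correlations and a normal selection model, and they run from nothing to roughly 0.1 to 0.2 SD at 20% withdrawal with moderate correlation. The rules should be changed before enrolment because the change is cheap and deleted data cannot be recovered.

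**What to change.** - **Sections 3.2 and 13.1:** separate stopping before the bracelets are applied (the participant may be replaced) from stopping after. Keep the target of 20 completers.
- **Reporting:** account for everyone fitted. Give the numbers fitted, completed and not completed, with timing and reason, beside the completer result.
- **Sections 13.3 and 13.4:** reconcile them so that baseline and partial data of a participant withdrawn by staff are kept unless the participant asks for removal.
- **Optional:** treat undone repeat tests as the worst outcome in a sensitivity analysis only. As the main analysis this would be debatable in a single-arm descriptive pilot, since stops unrelated to the device would count against it.

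The cost is some protocol wording and a line on the data form for the time and reason of stopping. The completer target and the single visit stay as they are, and clinical decisions on withdrawal are unchanged. The one downside for the sponsor is that the headline result may look slightly less favourable.

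### Sections 3.1 and 3.7 hide who is in the optional video clips, but no step hides whether the bracelets are on from whoever processes and measures them

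*Protocol*

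**What the plan says.** The study compares each participant before and while wearing the bracelets, in that order, within one session (Protocol 3.1 and 7.1). The 3.1 form item reads "Indicate if there is randomization, blinding, control group, etc". The response describes a pilot observational study and mentions no blinding.

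For participants who opt in to video, 3.1 says of each of the two recordings: "With the faces obscured, measurements of their gait/mobility will be performed using additional programs as indicated in the Data section". Section 3.7 fills this in. Clips are framed below the face and labelled with digits of the study code. Outside the app they are cropped, the app's stick figure is highlighted, and "the contrast and lighting of the video will be adjusted to make the subject look like a shadow". The stated aim is that "no features of the subject (such as clothing, gender, skin color, etc.) can be recognized".

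On extraction, 3.7 names "optical character recognition programs to analyze the joint angles numbers that the video recording provides", and adds: "Programs such as ImageJ will be used for feature extraction". Python or R then pulls the data.

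On the device, 3.1 says "we will apply these bracelets to a minimum of 1 patient per session" and that "a disposable sock will provide a physical barrier between the device and patient".

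**The concern.** The before versus while-wearing difference is the study's only performance contrast, and it has no control group. The staff who run a session cannot be masked as the study is designed, because they apply the bracelets and record the results themselves. Measurement of the clips comes afterwards and away from the participant, so condition could still be concealed there. The protocol already plans substantial image processing at that point, but directs it at privacy.

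If the person making processing choices knows the condition and expects improvement, a consistent tilt in those choices would pass straight into the mean paired difference. Nothing in the design could separate it from a device effect, and enrolling more participants would not reduce it. The named gait parameters in 3.7 come from video, and gait is part of the objective in 1.1, so the optional status of the video does not make the matter irrelevant.

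**Working it through.** The protocol gives no figure to reproduce here. The check sets each concealment step beside what it hides.

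1. **Faces obscured (3.1, once per recording; 3.7, by framing).** Hides identity. Does not hide condition.
2. **Digits of the study code as the app name (3.7).** Hides the name. Does not hide which of a participant's two clips came first. Because the order is fixed, anyone who knows which clip came first knows the condition.
3. **Crop and shadow silhouette (3.7).** The aim is that features of the subject cannot be recognized, and the examples given are clothing, gender and skin color. The silhouette may hide the bracelet incidentally, but the protocol neither says nor checks this. Foot angle is among the measured parameters, so the ankle region cannot simply be cropped away.
4. **Blinding (3.1).** The form item raises it and the response names none.

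Next, which measurement steps leave room for operator choice:

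- Stick figure: generated by the app, so little room.
- Joint angles: app numbers read by character recognition, so little room.
- Data pull by Python or R: automated as described.
- Cropping, and contrast and lighting adjustment: described without a fixed rule, so some choice is possible.
- ImageJ feature extraction: the text does not say how much of it is manual.

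The number of clips exposed depends on opt-in, which the protocol does not predict. Assuming one clip per condition, clips = 2 × participants opting in:

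- 10 opt in: 2 × 10 = 20 clips
- 15 opt in: 2 × 15 = 30 clips
- 20 opt in: 2 × 20 = 40 clips, the maximum under this assumption

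These counts show the work needed for the fix. They say nothing about the size of any bias, which cannot be derived from the document.

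**The case against.** The strongest reply is that this is silence and not error. The 3.1 item asks only whether there is blinding, the response claims none, and clip coding could sit in an analysis plan or reading manual. It is true that nothing is misreported. What stands is that concealing condition from the measurer is a matter of study conduct, and that 3.7 already sets out the concealment steps in detail but aims them all at identity.

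A second reply is that measurement is largely automated. This is right for joint angles and the stick figure, and it narrows the point to cropping, contrast adjustment and any manual ImageJ work.

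A third is that the list of hidden features is open-ended and a sock is clothing, so the silhouette may already cover it. That is a fair reading of the list. It does not cover a remaining bracelet or sock outline, or a measurer who knows which file came first.

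A fourth is that the video is optional, that study completion under 3.2 does not depend on it, and that this is a 20-person pilot with mainly descriptive analysis. This is correct, and it keeps the severity low.

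A reader might also infer that the researchers' prompts on stability and gait in 7.2 differ between conditions and so distort test performance. The document does not support this. The sentence does not show whether the prompts are questions or cues, it stands beside the questionnaires, the three tests use the same CDC tool in both conditions (7.3), and any uploaded script is not shown.

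**Conclusion.** The point holds in a limited form. The described processing hides participant identity, and no described step hides condition from whoever crops, adjusts and extracts measurements from the optional clips. The exposure is confined to steps with operator choice.

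A reader might infer that the video results will be biased, or that every gait parameter other than joint angles depends on the operator. The document supports neither: it describes no manual measurement step in detail and gives nothing from which a shift could be estimated. No size of bias is claimed.

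The conclusion rests on two readings: that the silhouette is not intended to conceal the bracelet, since its stated purpose concerns features of the subject, and that some operator choice exists in cropping, contrast adjustment or ImageJ. If all of these run under fixed automatic settings, little is left of the concern. Severity is low, and the change is worth making because it is cheap.

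**What to change.** Add to 3.7, in substance:

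- After the session, an existing team member who does not measure clips renames the exported clips with random codes that hide participant and condition.
- Clips are processed and measured in shuffled order, under one rule written before the first clip is measured and applied alike to both conditions.
- Where possible, clips are measured by a team member who did not run that participant's session.
- Any clip in which a bracelet or sock outline remains visible is noted.
- The code key, holding only study code and condition, is merged after measurements are locked.

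The cost is a few sentences, one code list and minor file handling for at most 40 clips (20 participants, one clip per condition). Section 12.2 already lists research assistants, data managers and statisticians. The key creates no new link to a name, because 13.4 states that consents are not matched to study codes. Renaming after the session leaves same-day removal under 13.3 possible. Nothing changes for participants.

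The change should be in place before the first clip is measured, since measuring again by someone who already knows the condition would not restore masking. Masking stays partial: on-site staff remain unmasked, an outline may still show, and with a small team the measurer may sometimes recognize a participant. The fixed order and the lack of a control are untouched.
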